3.1. Table of Tables

Table 10.1-1: Study Timeline 24
Table 11.1-1: Data Collection Schedule 27
Table 11.1-2: Data Collection Schedule for Subjects Requiring a Re-Surgery 28
Table 21.2-1: Adverse Event Definitions 55
Table 21.3-1: Criteria for Assessing Relationship of Study Device to Adverse Event 56
Table 21.4-1: Criteria for Assessing Relationship to Study Procedure 56
Table 21.5-1: Criteria for Assessing Relationship to Pelvic Floor 57
Table 21.6-1: Investigator Reporting Requirements 57

4. Introduction

Pelvic organ prolapse (POP) of the anterior and posterior vaginal wall, and vaginal apex, are among the most challenging and common aspects of traditional pelvic reconstructive surgery. As life expectancy increases, significantly greater numbers of women will present with POP and stress urinary incontinence (SUI) requiring surgical intervention. Women face an 11% lifetime risk of requiring major surgery for POP.³

The main goal of POP surgery is restoration of normal anatomy to achieve proximal vaginal suspension, mid-vaginal lateral attachments and distal vaginal fusion to the urogenital fascia and perineum. Women undergoing pelvic reconstructive surgery for POP hope to achieve relief of symptoms, restoration of normal anatomy, maintenance of vaginal capacity for sexual function and improvement in the quality of life.

The difficulties associated with repair of cystocele were cited by Ahfelt as early as 1909, and reinforced nearly a century later by Weber et al. (2001) who reported recurrence rates as high as 70% in a widely cited randomized controlled study (RCT).⁴ Clark et al. estimated that up to 60% of surgical recurrences occur at the same anatomic site as the original repair, highlighting the limitations associated with plicating and/or suspending weakened connective tissues to one another.¹ In recent years, surgical methods such as vaginal mesh repair (VMR) have become available as an option for treating more advanced and challenging cases.

Biologic grafts like Xenform offer potential advantages over synthetic meshes. These include the capability for in-vivo tissue remodeling and consequent reduction in the rates of extrusion and/or erosion¹⁰. Goldstein, et al.² studied Xenform and showed an 88% success rate when patients were followed for one (1) year.

5. Device Description

Xenform Soft Tissue Repair Matrix is intended for use as a soft tissue patch to reinforce soft tissue where weakness exists and for the surgical repair of damaged or ruptured soft tissue membranes. Xenform is specifically indicated for the repair of colon, rectal, urethral and vaginal prolapse, and procedures such as sacrocolposuspension and urethral sling.

Xenform is derived from fetal bovine dermis. It is predominantly Type I and Type III collagen. Other versions of the same processed fetal bovine dermal material have been used to treat over 250,000 patients in soft tissue repair applications, including repair/replacement of the dura, repair/reinforcement of tendons, wound closure, hernia repair and general plastic and reconstructive surgery.

When hydrated, Xenform is pliable, strong and tissue-compatible because it is derived from animal tissue. Xenform is not chemically cross-linked like some other biologic grafts but relies on the inherent strength of the bovine dermis from which it is derived. It is easily vascularized and is thought to remodel into a native tissue-like structure.

Xenform has been used in over 30,000 patients, worldwide, and there have been no complaints of tissue erosion, tissue perforation, or infection to-date.

6. Study Objectives

The primary objective is to evaluate clinical effectiveness of transvaginal repair with Xenform against traditional native tissue repair in women surgically treated for anterior and/or apical pelvic organ prolapse. Secondary objectives are to evaluate Xenform-related complications and subject reported outcomes.

7. Study Endpoints

7.1. Primary Endpoints

The primary endpoint of the study is to achieve non-inferiority of transvaginal repair with Xenform over native tissue repair at 36 months as compared to baseline.

Success will be based on a composite of objective and subjective measures, and subjects will be considered a surgical success if each of the three criteria is met:

1. Subjective success is achieved if the patient denies symptoms of vaginal bulging per PFDI-20 question 3, answering “no” or “yes” but “Not at all” bothersome (<2).
2. Anatomic success (in the operated compartment):
 - Anterior segment: Leading edge of anterior prolapse is at or above the hymen or POP-Q point Ba \leq 0.
 - Apical segment: The vaginal apex does not descend more than one-half into the vaginal canal (i.e. POP-Q point C < -1/2 TVL) for multi-compartment prolapse or POP-Q point C \leq 0 for single compartment apical prolapse.
3. No retreatment for POP: No additional surgical treatment for POP in the segment(s) of the vagina treated at the index surgery or no pessary use since index surgery (i.e., ‘treated segment’ refers to the target compartments in this study, which are the anterior and apical compartments).

Additionally, a co-primary endpoint of the study is to achieve non-inferiority of transvaginal repair with Xenform to native tissue repair for safety by comparing rates of serious device or serious procedure related complications between baseline and the 36 month time point. Serious injury is defined per 21 CFR 803.3, i.e., life threatening, results in permanent impairment of a body function or permanent damage to a body structure or injury or illness that requires medical or surgical intervention to preclude impairment of a body function or permanent damage to a body structure.

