³Assessments include cystoscopy (at discretion of surgeon), estimated blood loss (EBL), assessment of concomitant procedures, and assessment of anesthesia type and duration of procedure.

⁴Post-Operative Assessments include assessment of infection (wound, vaginal, bladder), voiding status, and date and time of discharge.

⁵Assessment of Risk Factors includes menopausal status, estrogen use, age, smoking, diabetes status, BMI, hysterectomy status, concomitant procedures, surgeon training and experience.

⁶All serious and non-serious device, procedure, and pelvic floor-related events, any other relevant events pertaining to the pelvic region, and any events resulting in death will be collected.

⁷Every effort should be made to do the follow-up visit within the window; however, if this is not possible, the site should attempt to complete the visit as soon as possible but before the next visit window opens. Follow-up visits will be considered missed once the visit window for the next follow-up visit opens. For the Month 36 visit, the visit is not considered missed until the last day of the visit window.

If a subject requires a re-surgery during the study, please refer to the reduced table below for follow-up assessments. Subjects undergoing re-interventions (non-surgical) continue with the study schedule as noted in Table 11.1-1. Additional data will be collected on subjects requiring a re-surgery, including a second procedure, Xenform removal (as applicable), and second hospital discharge. All subjects who are re-operated on will continue with their follow-up schedule until 36 months post their initial study procedure.

Table 11.1-2: Data Collection Schedule for Subjects Requiring a Re-Surgery

Procedure/Assessment	Screening/ Enrollment Visit	Pre- Operative/ Baseline Visit	Surgery (≤3 mos from Baseline)	Discharge	Post-Operative Follow-up Visits (± 4 Weeks)				
					Month 2 Visit (± 4 Weeks)	Re-Surgery	Discharge	Next Scheduled Follow-up Visit (-4/+12 Weeks)	Month 36 Visit* (-4/+12 weeks)
Informed Consent	X							After a re-surgery, subjects will return to the clinic on the date of their next regular study visit per the Schedule of Events table above. Subjects will continue to return for all scheduled Follow-up Visits until 36 months post their initial study procedure.	
Inclusion/Exclusion Criteria Review	X								
Demographics		X							
Urine Pregnancy Test	X	X							
Physical Examination		X							
Medical History ¹		X							

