Pelvic Exam with vaginal length measurement		X			X				X
Assessment of infection (vaginal, bladder)				X	X		X		X
Prolapse Grading (POP-Q Scoring)		X			X				X
PFDI-20 (Pelvic Floor Symptoms)		X			X				X
PFIQ-7 (Quality of Life)		X							X
PISQ-12 (Sexual Functioning)		X							X
PGI-I for Prolapse (Patient Improvement)									X
TOMUS Pain Scale		X			X				X
SSQ-8 for Surgical Satisfaction									X
EQ-5D for Health Status		X							X
Procedure and Assessments ³			X			X			
Post-Operative Assessment ⁴				X					
Assessment of Analgesic Intake		X			X				X
Assessment of Adverse Events ⁶			X	X	X	X	X		X
Assessment of Risk Factors ⁵		X			X			X	
End of Study								X	

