11.4.7. Months 6 (± 4 weeks), 12, 18, 24, 36 Visits ($-4/+12$ weeks)

- Pelvic exam with vaginal length measurement
- Assessment of infection (vaginal, bladder)
- Prolapse grading (POP-Q Scoring)
- Assessment of pain (TOMUS pain scale) and analgesic intake
- PFDI-20

- PFIQ-7
- PISQ-12
- PGI-I for Prolapse
- SSQ-8 for surgical satisfaction (Months 6, 12, 24, 36 only)
- EQ-5D for health status (Months 12, 24, 36 only)
- Assessment of adverse events (device, procedure, and pelvic floor related)
- Assessment of risk factors
- Study completion (Month 36 only)

All subjects who have completed the study surgery and discharge will proceed to be followed through the above-outlined study visits to Month 36 where the primary endpoint analysis will be achieved when the last subject completes this visit. All subjects completing the Month 36 visit will be considered to have completed the study.

11.5. *Re-Intervention/Re-Surgery*

It is the intention of this study to demonstrate an improvement in anterior/apical pelvic organ prolapse through clinical effectiveness of transvaginal prolapse repair with Xenform. However, it is recognized that during the course of the study, there is a possibility subjects may require a medical re-intervention for events including but not limited to failed prolapse repair, persistence of prolapse symptoms, or Xenform or procedure-related complication. A re-intervention may include surgical or non-surgical treatments and can occur for a medical complication or for prolapse recurrence. For the purpose of this study surgical interventions shall be classified as “re-surgery” and non-surgical interventions shall be classified as “re-interventions”. Analyses will be performed to compare the rate of office-based interventions and of surgical interventions for medical complications and for prolapse recurrence in both treatment groups.

Non-surgical interventions (re-interventions) are defined as office-based procedures and do not involve an operating room procedure. Examples of non-surgical interventions may include but are not limited to an office visit to trim exposed Xenform or suture in the vagina, a pessary, or physical therapy to treat procedural complications or persistent prolapse symptoms. Data on non-surgical interventions will be captured in the CRFs. Subjects will continue to be followed per the regular study visit schedule.

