Surgical interventions (re-surgery) are surgical operations performed to correct recurring prolapse symptoms, a procedural complication, or Xenform-related complication. These surgical events typically may occur on an outpatient basis yet can require admission to a hospital. The decision to perform a re-surgery for failed prolapse repair or persistence of prolapse symptoms will be per physician and subject discretion and all re-surgery data will be captured in the Case Report Forms. All subjects defined as having a prolapse recurrence will be those who have anatomic and symptomatic failure of their prolapse surgery (prolapse beyond the hymen and symptoms of vaginal bulge).

Subjects undergoing a re-surgery will be followed to 36 months post their initial study procedure as indicated in Table 11.1-2. The subject should return to the clinic for the next regular study visit as per her original schedule. If the subject elects to not undergo re-surgery, then the subject will be followed to the Month 36 visit unless the subject chooses to withdraw consent from the study. No subject will be followed for more than 36 months beyond their initial study procedure.

11.6. *Subject Death*

If any serious adverse event results in death (regardless of relatedness to the study device, procedure, or pelvic floor), the event is to be documented in the source documentation, Case Report Form, and reported to the Sponsor within the timeframe noted in Table 21.6-1 (Investigator Reporting Requirements). If an autopsy is conducted, a copy of the final autopsy report should be submitted to the Sponsor or designee. The primary objective of the autopsy is to determine the cause of death, complications and other relevant findings.

12. Statistical Considerations

12.1. *Endpoints*

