12.1.2. Secondary Endpoints

Secondary endpoints will be to evaluate Xenform-related complications and subject reported outcomes as safety endpoints between baseline and 36 months:

1. Incidence of Xenform erosion
2. Incidence of Xenform exposure
3. Incidence of de novo dyspareunia
4. Improvement in subject specific outcomes at 36 months compared to Baseline (pelvic floor symptoms (PFDI-20), QOL (PFIQ-7), sexual functioning (PISQ-12), TOMUS pain scale)
5. Assessment of subject's level of improvement, measured by the Patient Global Impression of Improvement for Prolapse (PGI-I for Prolapse)
6. Absence of re-intervention or re-surgery for recurrence or persistence of POP or Xenform exposure/erosion
7. Surgical success based on the following composite outcome:
 - a. Subjective success: patient denies symptoms of vaginal bulging per PFDI-20 question 3, answering "no" or "yes" but "Not at all" bothersome (<2)
 - b. Anatomic success (in the operated compartment):
 - Anterior Segment: No anterior prolapse at or beyond the hymen or POP-Q point Ba<0
 - Apical Segment: The vaginal apex does not descend more than one-half into the vaginal canal (i.e. POP-Q point C < 1/2 TVL) for multi-compartment prolapse or POP-Q point C < 0 for single compartment apical prolapse.
 - c. No retreatment for POP (treated segment): No additional surgical treatment for POP in the segment(s) of the vagina treated at the index surgery or no

nessary use since index surgery ('treated segment' refers to the target compartments in this study, which are the anterior and apical compartments)

8. Device or procedure related incidence of the following: pelvic pain, infection, vaginal shortening, atypical vaginal discharge, neuromuscular problems, vaginal scarring, de novo vaginal bleeding, fistula formation and/or de novo voiding dysfunction

Definitions for the above listed adverse events are included in Section 21.2 (Definitions and Classifications). Rates of incidence for the adverse events will be stratified by primary or recurrent prolapse in both treatment groups.

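### The retreatment criterion in the primary composite says *or* where its heading needs *and*: read literally, only a woman with both repeat surgery and a pessary fails it

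*Combined protocol and SAP*

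**What the plan says.** Section 7.1 defines the primary effectiveness endpoint as a composite of bulge symptoms, anatomy and retreatment, and states that "subjects will be considered a surgical success if each of the three criteria is met". The third criterion carries the label of no retreatment for prolapse and is spelled out as "No additional surgical treatment for POP in the segment(s) of the vagina treated at the index surgery or no pessary use since index surgery". The Synopsis repeats it. Secondary endpoint 7c uses the same construction in the Synopsis, Section 7.2 and Section 12.1.2, where it begins "No additional surgical treatment for POP in the segment(s) of the vagina treated at the index surgery or no" and continues to pessary use.

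Retreated women stay under observation. On re-surgery, Section 11.1 says: "All subjects who are re-operated on will continue with their follow-up schedule until 36 months post their initial study procedure". Table 11.1-2 schedules POP-Q and PFDI-20 for them at Month 36. For non-surgical interventions, Section 11.5 lists "an office visit to trim exposed Xenform or suture in the vagina, a pessary, or physical therapy" as examples and adds: "Subjects will continue to be followed per the regular study visit schedule".

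The Synopsis says that analyses follow the Statistical Analysis Plan. Section 12 of the text supplied contains no separate rule for scoring criterion 3.

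On the separate minor point, the multi-compartment apical threshold is C < -1/2 TVL in the primary endpoint (Synopsis, Section 7.1). In secondary endpoint 7 it is C < 1/2 TVL (Synopsis, Sections 7.2 and 12.1.2).

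**The concern.** A criterion of the form (no surgery) or (no pessary) is met as soon as one of the two is absent. That contradicts the label, under which either form of retreatment should be a failure. The other two criteria do not catch the error. Repeat surgery or a pessary is meant to correct symptoms and anatomy, so a retreated woman may well satisfy both at Month 36.

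This rule helps decide who is a success in the primary non-inferiority test. It also matters earlier. Section 12.3.8 plans an interim analysis that covers the primary endpoint, and Section 12.3.8.1 tests the composite at 12 months to support premarket approval review. The interim code is therefore the first place where the wording is applied.

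**Working it through.** **1. Truth table for criterion 3.**

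| History | As written: no surgery *or* no pessary | Per heading: no surgery *and* no pessary |
|---|---|---|
| Neither | met | met |
| Surgery alone | met | not met |
| Pessary alone | met | not met |
| Both | not met | not met |

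As written, 1 of 4 histories fails. Under the heading, 3 of 4 fail. The *or* appears in 5 of 5 listings, so no correct version exists elsewhere to override it.

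**2. The planned sample size does not depend on this.** Inputs from Section 12.1.1.2: 70% success (taken as equal in both arms), margin 12%, type I error 0.05 (one-sided, matching the two-sided 90% interval in Section 12.1.1.3), power 80%, loss to follow-up 20%.

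- n per arm = (1.645 + 0.842)² × (2 × 0.70 × 0.30) / 0.12² = 6.18 × 0.42 / 0.0144 ≈ 180.3, rounded up to 181. This reproduces the plan.
- 181 / 0.80 = 226.25, rounded up to 227. This also reproduces the plan.

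Criterion 3 enters neither step.

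**3. Effect of one reclassified woman, unadjusted.** 100/227 = 0.44 points on the planned enrolled number; 100/181 = 0.55 points on the planned evaluable number. Neither figure reflects the propensity strata of Section 12.2.3.

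**4. How many women could change status (assumed rates).** The documents give no surgery or pessary rates for recurrence. With s, p and b the percentages with surgery, with a pessary and with both, failures are s + p − b under *and*, and b under *or*. The difference is s + p − 2b.

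| s | p | b | Fail, *and* | Fail, *or* | Difference | Of 181 |
|---|---|---|---|---|---|---|
| 2 | 2 | 0 | 4 | 0 | 4 | 7.2 |
| 5 | 3 | 0.5 | 7.5 | 0.5 | 7 | 12.7 |
| 8 | 5 | 1 | 12 | 1 | 11 | 19.9 |
| 10 | 6 | 2 | 14 | 2 | 12 | 21.7 |

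These are upper limits for the composite, because a woman must also meet criteria 1 and 2 to become a success.

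**5. What an imbalance would do (assumed, illustration only).** Suppose the true rates under the heading's meaning are 70% control and 58% Xenform, exactly at the margin. Suppose the literal rule adds g more points of successes to Xenform than to control. With 181 per arm, the chance of concluding non-inferiority is Φ(g/SE − 1.645), where SE = √[(0.70 × 0.30 + q(1 − q))/181] and q = 0.58 + g.

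- g = 0: 5%
- g = 2 points: 11%
- g = 4 points: SE = √[(0.21 + 0.2356)/181] = 0.0496, so Φ(0.806 − 1.645) = 20%
- g = 6 points: 33%
- g = 8 points: 50%

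An excess in the control arm works the other way. Sections 12.3.1 and 12.3.2 hypothesise fewer interventions for recurrence with Xenform. If that is true, the literal rule would tend to favour control.

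**6. Timing (Table 10.1-1).** Last subject enrolled December 2016, plus 12 months, gives December 2017. Adding the 12-week window gives late February to late March 2018. The expected final lock is February 2020, about two years later.

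**7. The missing minus sign.** It is present in 2 of 2 primary listings and absent in 3 of 3 secondary listings. The printed rule accepts any C below +TVL/2, so it wrongly passes values from −TVL/2 up to +TVL/2. For assumed TVL:

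- 6 cm: −3 to below +3 cm
- 8 cm: −4 to below +4 cm
- 10 cm: −5 to below +5 cm

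Multi-compartment entry in Section 9.2 requires C ≥ −1/2 TVL. A woman whose apex has not moved since baseline could therefore pass this apical limit.

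**The case against.** The best reply is that this is loose English. Under a heading that says no retreatment, most readers take no A or no B to mean neither. The protocol does not use *and* and *or* strictly elsewhere: secondary endpoint 6 joins re-intervention and re-surgery with *or* in the Synopsis and Section 12.1.2, but with *and* in Section 7.2. A coding specification outside the supplied text may already apply the intended rule, and no effect on the result has been shown.

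Much of this is fair. Neither is the likely intent. Section 11.5 points the same way when it describes women with recurrence as "those who have anatomic and symptomatic failure of their prolapse surgery", though that does not settle Month 36 scoring. Nothing shows that the code follows the literal text. But inconsistent use of the two conjunctions is a reason to write the rule down, because code applies the operator it is given and no listing states the intended rule. The lack of a computed effect reflects missing retreatment rates and is not evidence that the effect is nil.

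Two smaller points also stand. The primary analysis is intention-to-treat with imputation, so 0.44 points per woman is the nearer figure. Late 12-month visits may be accepted until the Month 18 window opens (early May to early June 2018 for the last enrolled), so March 2018 is only the end of the nominal window.

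**Conclusion.** The concern holds. Criterion 3, in all five listings, is worded so that only the combination of repeat surgery and pessary use fails, which contradicts its own heading. It should be fixed because it is a scoring rule for the primary endpoint. The effect on the treatment difference is unknown and is zero if reclassified shares are equal by arm. What can be stated from the plan is 0.44 to 0.55 points of unadjusted success rate per reclassified woman. The counts and probabilities in steps 4 and 5 of the working rest on assumed rates. If the code already treats either event as a failure, no result changes.

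The missing minus sign is a separate and minor error. The printed threshold contradicts both its adjoining description and the primary threshold. It affects only a reported secondary success rate, with no hypothesis, margin or sample size attached (Sections 12.1.2.1 and 12.1.2.2). The number of women in the affected band is unknown.

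**What to change.** - In the Synopsis (primary and secondary), 7.1, 7.2 and 12.1.2, reword the retreatment criterion to: *no repeat prolapse surgery in a treated segment and no use of a pessary since the index operation; either event is a failure*.
- Check the 12-month interim code and the final analysis code against that rule, and document the check before the final database lock, expected in February 2020.
- Under the reworded rule, reconcile the logistic regression in Section 12.3.4, which uses office-based intervention for recurrence as a covariate for the primary endpoint. A pessary counts as such an intervention, so the covariate would partly determine the outcome.
- In secondary endpoint 7, change C < 1/2 TVL to C < -1/2 TVL in the Synopsis, 7.2 and 12.1.2.

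The cost is a wording amendment with the approvals that Section 14 requires, and a code check. If the interim code followed the literal rule, the interim success tables must be re-run. No new data are needed, because Section 11.5 already has both kinds of intervention captured in the case report forms.
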